- 2. Patients with Type 1 diabetes and non-painful diabetic peripheral neuropathy (DPN)
- 3. Patients with Type 1 diabetes and without diabetic peripheral neuropathy (DPN).
- 4. Healthy control subjects matched for age, BMI, and gender.

Diabetes duration, HbA1c, insulin use, ethnicity, and co-morbidities will be matched between group 1, 2 and 3 to best ability.

Inclusion criteria:

- 1. Men and women minimum 18 years of age and maximum 70 years of age
- 2. Signed informed consent form
- 3. Diagnosed with diabetes type I (for group 1-3)
- 4. Diagnosed with DPN defined as a threshold above 25-volt biothesiometry or absent feeling on the big toe using 10g-monofilament. (for group 1-2)
- 5. Answered questionnaire: PainDETECT
- 6. Nothing abnormal on initial tests (group 4)
- 7. Accepted initial screening blood samples
- 8. MRI-compatible participant

Exclusion criteria:

1. Current or previous alcohol- or drug abuse

- 2. Abnormal screening blood samples
- 3. Not being able to understand Danish written and/or verbally
- 4. Not being able to corporate to examination (e.g. not being able to speak, suffering from senile dementia etc.)
- 5. Previous chemotherapy or intake of experimental medicine
- 6. Active HSV- or VZV-infection or known HIV
- 7. Known severe skin disease
- 8. Known neural damage or disease in the neural system (e.g. MS, Guillain-Barre etc.)
- 9. Critical limb ischemia defined as in current clinical consensus[63]
- 10. Allergy or intolerance to histamine or inability to make do without for one day
- 11. Pregnancy
- 12. Active cancer-disease

C. Assessment of Resources

The study will be conducted in collaboration with Steno Diabetes Center Northern Denmark (SDCN) and Department of Radiology, Aalborg University Hospital. SDCN has access to patients with diabetes and can provide the necessary premises.

The study will be conducted in collaboration with Center for Neuroplasticity and Pain (CNAP), Aalborg University and SDCN, who have the technical and financial resources needed to establish the setup and conduct the examinations. Furthermore, an experienced research Bio. Med. Lab. Technologist is signed for the project thereby, alongside the Ph.D.-students, ensuring trained personnel. The study is set for a long inclusion, but additional time is available if required, as the Ph.D.-students are employed until 31st of October 2022.

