The project is initiated by [name], Aalborg University and SDCN, and is supported economically by Steno Diabetes Center North Denmark and Aalborg University. The support is however limited to staff salary and purchase of smaller equipment.

D. Study Procedures

Diabetic patients will be recruited during their scheduled visit to the outpatient clinic of SDCN, Aalborg University Hospital. Healthy controls will be recruited based on the included diabetic population using relatives of diabetic patients, medical students, and people known by participating staff.

After the informed consent is obtained the screening of the participant will be executed. Afterwards the participant have to attend three different sessions as shown in appended flowchart. Each session includes different tests and the sessions will be ordered randomly, since they have no influence on each other. Moreover, a conventional nerve conduction test will be performed, however this test will be performed as per usual by the department of neurophysiology, as this is a standard examination for patients with neuropathy.

PainDETECT

PainDETECT is an English questionnaire validated for detecting neuropathic pain[64]. It has later been translated and validated in Danish[65], and will be given each participant alongside instructions after form of consent has been signed. The patients will answer the questionnaire individually and will need to complete this before any other examinations can be conducted, as this will help placing the patients in the correct group.

Estimated time: 5-15 min.

Clinical examination

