The blood samples will be taken and handled as usual by the biochemical department and will be destroyed after usage. No biobank will be made. All samples will start being analyzed immediately (within 2h), however, some samples (like vitamin D) will take some time to analyze. All results will be available within 10-12 days but samples will always be destroyed as soon as the analysis has been initialized.

V. DATA COLLECTION

Patient data will be collected using the electronic patient journal (EPJ) after consent of the participant. Only patients with an active continuity of care at SDCN will be included (as well as healthy controls). The principle investigator is employed at SDCN as a medical doctor alongside one of the Ph.D.-students.

Data collected will include demographic data such as name, age, sex, weight, and height, and clinical information related to diabetes, such as type, duration, medication, complicating peripheral arterial disease, and status of complications. This to ensure correct grouping of the patients and to make sure that they meet the inclusion criteria.

VI. DATA ANALYSIS

A. Sample Size Considerations

The following sample size estimation is made on the ability to separate a group of diabetic patients without neuropathy from a group of diabetes patients with 'moderate' neuropathy. The calculations are based on published measurement of the sensory nerve action potential amplitude in nerve fiber conduction assessments[45]. Setting the significance level to 0.05 and the power to 0.8 results in a sample size estimation of 16 persons in each group. $n = \frac{15.7*\sigma^2}{d^2} = \frac{15.7*(4.7^2+7.5^2)}{(14.4-5.7)^2} = 16$. The study involves several experiment measures, but we expect that max 20% of the measures will be dropouts. The number of participants needed to be recruited in each group will therefore be $N = \frac{n}{1-dropout} = \frac{16}{0.8} = 20$. We want to compare four groups as defined in section IV.B. Study Population. The total number of participants will therefore be 80.

B. Statistical Methodology

The data will initially be analyzed by a series ANOVA test to compare each measurement between the four groups.

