To avoid 'mass significance' a combined analysis of all measurements will be performed by logistic regression models (LRM) in three steps. This will allow an estimate of the odds ratio and accuracy of each of the measurements and the measurements in combination. First, a series of univariate LRM will be performed for each measurement to investigate the odds ratio and accuracy of the individual. Second, a multiple factor LRM with all measurements as factors will be performed to estimate the odds ratio and accuracy for all measures in combination. Thirdly, factor reduction will be performed to assess the accuracy and odds ratio of a set of independent measures.

Simple bivariate correlation will be performed to further investigate the relation between measurements. Due to the complexity of the measurements a further analysis of the interdependency of the measures using factor analysis will be performed.

VII. DATA AND SAFETY MONITORING PLAN

The project will be reported to the Data protection Agency (DPA), and all sensitive data will be stored in either Red-CAP or on the protected server of Aalborg University Hospital, *"Elektronisk system adgang"* (ESA).

Data are stored in accordance with the stipulations in The Danish Personal Data Protection Act (Persondataloven) and other relevant Danish legislation. If any data processing would occur in foreign countries, the data will be anonymized and handled according to the Danish Data Protection Act.

The data can only be used for the interpretation of this project and will therefore not be of interest to third party.

The project is included in "Region Nordjyllands fællesfortegnelse".

VIII. STUDY LIMITATIONS

Both PTT and QST require corporation from the patients and include subjective measures of pain. As the measured thresholds are not purely objective, psychosocial factors might influence test results.

The study includes diabetic patients exclusively and might not be applicable on populations with different causes of neuropathy.

The expected number of participants are set at 80, thus maybe require additional larger studies to confirm findings.

IX. ETHICAL CONSIDERATIONS

A. Informed Consent

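### Section VI.B compares groups and estimates odds ratios without covariates although groups 1-3 are not matched on age or sex, so an age gap could bias DPN versus no DPN either way

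*Combined protocol and SAP*

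**What the plan says.** Section VI.B (Statistical Methodology) starts with group comparisons: "The data will initially be analyzed by a series ANOVA test to compare each measurement between the four groups". It then turns to logistic regression: "First, a series of univariate LRM will be performed for each measurement to investigate the odds ratio and accuracy of the individual". A multiple model containing all the measurements and a reduced model follow. No step names age, sex or any other covariate, and the outcome of the logistic models is not stated.

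Section IV.B (Study Population) describes group 4 as "Healthy control subjects matched for age, BMI, and gender". For the diabetic groups it says: "Diabetes duration, HbA1c, insulin use, ethnicity, and co-morbidities will be matched between group 1, 2 and 3 to best ability". Age and sex are not on that second list. The eligible range is wide: "Men and women minimum 18 years of age and maximum 70 years of age".

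Section IV.D (Study Procedures) has no step that balances age: "Diabetic patients will be recruited during their scheduled visit to the outpatient clinic of SDCN". Controls are chosen afterwards: "Healthy controls will be recruited based on the included diabetic population".

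Section V (Data Collection) confirms that the covariates will be available: "Data collected will include demographic data such as name, age, sex, weight, and height". Their stated purpose is correct grouping and eligibility, not analysis. Section VIII (Study Limitations) does not mention confounding.

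**The concern.** By matching controls on age and gender, the plan accepts that these factors can matter. Yet matching controls to the diabetic patients does not make groups 1, 2 and 3 alike. Matching on diabetes duration may narrow an age difference but cannot guarantee its absence, because patients with equal duration can differ in age at onset.

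The exposed contrast is the central one. Section VI.A sizes the study on separating diabetic patients with and without neuropathy, and Section IV.A makes the sensitivity and specificity of every examination the main endpoint. If patients with DPN are older, a test that worsens with age gains apparent accuracy. If they are younger, a useful test loses it. Tests differ in how strongly they depend on age, so their ranking could also be distorted.

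**Working it through.** **The plan's own figure.** Section VI.A gives n = 15.7 × (4.7² + 7.5²) / (14.4 − 5.7)² = 15.7 × 78.34 / 75.69 = 16.25, stated as 16. Then 16 / 0.8 = 20 per group and 4 × 20 = 80. This reproduces, and the present point does not change it. The sized effect in SD units is 8.7 / √(78.34 / 2) = 8.7 / 6.26 = 1.39.

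**Assumed inputs.** The documents give no age SD, age gap or age slope. I therefore assume that:
- groups 1 and 2 differ in mean age from group 3 by g within-group SDs, with g from 0.25 to 0.75;
- the measurement has within-group SD 1 and correlation r with age, r being 0.3 or 0.5;
- controls sit at the mean age of the diabetic patients (IV.D recruits them to fit that population);
- the logistic outcome is DPN versus no DPN among diabetic patients.

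The bias in the DPN contrast is b = r × g.

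**ANOVA with no true effect.** The group means are b, b, 0 and 2b/3, with overall mean 2b/3. The squared deviations sum to b²(1/9 + 1/9 + 4/9 + 0) = 2b²/3, so the noncentrality is λ = n × 2b²/3. The rejection rate comes from the noncentral F distribution with 3 and 4n − 4 degrees of freedom. For g = 0.5, r = 0.5 and n = 20, b = 0.25, λ = 20 × 2 × 0.0625 / 3 = 0.83, and the rate is 10.1%.

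**Logistic models with no true effect.** These are simulated with a likelihood-ratio test, 10,000 runs per case. The odds ratio is the median per SD of the measurement.

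**AUC with no true effect.** AUC = Φ(b/√2). The table gives simulated values, which agree within 0.001.

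| g, r | b | ANOVA false positives, 20 / 16 per group | Odds ratio | Logistic false positives, 40 v 20 / 32 v 16 | AUC |
|---|---|---|---|---|---|
| 0.25, 0.3 | 0.075 | 5.4% / 5.3% | 1.08 | 6.5% / 6.5% | 0.52 |
| 0.5, 0.3 | 0.15 | 6.7% / 6.4% | 1.16 | 9.0% / 8.7% | 0.54 |
| 0.5, 0.5 | 0.25 | 10.1% / 9.0% | 1.29 | 15.9% / 13.8% | 0.57 |
| 0.75, 0.5 | 0.375 | 17.5% / 14.6% | 1.46 | 27.9% / 24.0% | 0.60 |

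With age and sex in the linear model, false positives are 4.8% to 5.2%. With age in the logistic model, the odds ratio is about 1.00 and false positives are 5.6% to 6.2%. The age-adjusted AUC is 0.50. For scale, the sampling SD of one AUC at 40 v 20 is about 0.08.

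**A true effect of 0.5 SD.** With no gap, AUC = Φ(0.5/√2) = 0.64. A gap of 0.5 SD in either direction gives Φ((0.5 ± b)/√2):
- r = 0.3 (b = 0.15): 0.60 to 0.68;
- r = 0.5 (b = 0.25): 0.57 to 0.70.

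After age adjustment, the AUC is about 0.65 (r = 0.3) or 0.66 (r = 0.5) whichever way the gap runs. Power of the univariate logistic test at 40 v 20 is 45% with no gap. When the gap runs against the effect, it is 25% (r = 0.3) or 15% (r = 0.5), against 46% and 54% age-adjusted.

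**Relative to the sized effect.** The bias of 0.075 to 0.375 SD is 0.075/1.39 = 5% to 0.375/1.39 = 27% of it.

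**The case against.** The strongest reply is that no bias has been shown. Every input beyond the sample size is assumed. If age were unrelated to group, the SD of the gap at 40 v 20 would be √(1/40 + 1/20) = 0.27, so chance would produce a gap above 0.25 SD in 36% of studies, above 0.5 SD in 7% and above 0.75 SD in 0.6%. The larger cases thus mostly need a systematic age difference, which the documents do not establish. This stands as a limit on the size. It does not remove the gap in the plan.

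Second, the effect is modest over much of the range. The logistic test rejects about 5.5% of the time even with no gap, so age adds about one percentage point in the mildest case. This also stands.

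Third, the logistic figures depend on an outcome that the plan leaves open. If controls join the non-DPN side (40 v 40), the odds ratios are 1.05, 1.11, 1.19 and 1.29, and false positives 6.0%, 7.5%, 11.8% and 20.0%. These are smaller, but in the same direction.

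Fourth, diagnostic accuracy is normally reported unadjusted, and an age-adjusted AUC answers a different question: with r = 0.5 and no gap, it is 0.66 against 0.64. This is right, and it is why the adjusted AUC is proposed only as a sensitivity analysis.

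Fifth, no effect of sex is quantified. The case for sex rests only on the plan's own choice to match controls on gender.

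Finally, age and sex could be added to the matching list for groups 1-3. That could help, but it changes recruitment, and matching only as far as possible would still leave residual differences.

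**Conclusion.** The concern holds. VI.B uses no covariate, and the matching of groups 1-3 omits age and sex; both are plain in the text. Whether bias will arise, and how much, cannot be settled from the documents. In the assumed range, false positives run from close to nominal up to 17.5% for the ANOVA and 27.9% for the logistic test, and an AUC can shift by up to about 0.10 from its no-effect value of 0.50. The upper figures need a 0.75 SD gap and a correlation of 0.5.

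For the 1.39 SD nerve conduction effect, the risk to the conclusion is small. It matters more for newer tests, such as perception threshold tracking and MRI, if their effects are smaller; the plan gives no effect size for them. The change should be made because it is cheap and the data are already there. Confidence is medium, because the size rests on assumptions.

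**What to change.** Amend VI.B as follows.

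1. Replace each per-measurement ANOVA with a linear model containing group, age and sex, and report age and sex by group.
2. State the outcome of each per-measurement logistic model, for example DPN versus no DPN among diabetic patients. Report an age-adjusted odds ratio beside the unadjusted one. Leave sex out of these models.
3. Keep unadjusted sensitivity and specificity as the primary report. Add an age-adjusted AUC for each test as a sensitivity analysis: subtract the within-group age slope, then compute the AUC in the diabetic patients. Say that it describes how well the test separates patients of the same age.
4. Leave the model with all measurements unchanged.

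This takes three or four sentences, with no new data and no change to recruitment. The linear models lose two error degrees of freedom (80 − 4 = 76 becomes 74; with 16 per group, 64 − 4 = 60 becomes 58). For a measurement unrelated to age and a 0.5 SD gap, about 6% to 7% of precision is lost, and the SD of the AUC rises by about 5% (0.079 to 0.083 at 40 v 20; 0.089 to 0.093 at 32 v 16). With DPN versus no DPN as outcome, test plus age leaves 20/2 = 10 non-DPN patients per predictor, or 16/2 = 8 after dropout, which is why sex stays out of the logistic models.

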
III. STUDY OBJECTIVES

To test Perception Threshold Tracking (PTT) and multi-level MRI as methods for early detection and grading of severity of neuropathy in patients with diabetes mellitus.

To use multi-level MRI for characterization of peripheral and central nervous system changes related to neuropathy in patients with diabetes mellitus.

To compare Perception Threshold Tracking (PTT) and MRI to methods of traditional clinical practice and established methods of clinical research like Corneal Confocal Microscopy (CCM) and Quantitative Sensory Testing (QST) as well as axon flair-mediated neurogenic vasodilation (AF).

To test reliability of different measurements of neuropathy.

A better understanding of the underlying neuropathy of diabetes and new methods for early, reliable detection of DPN could result in intensified treatment and prophylactic measures prolonging of the complicationfree period of diabetes mellitus. Ultimately, this could potentially result in fewer complications related to the diabetic foot, and maybe even prolonged overall-survival and reduced healthcare cost.

IV. METHODS

A. Study Design

This study is a prospective, observational, cross-sector study starting March 1, 2019 running until December 1, 2021. The study will be conducted on patients from Aalborg University Hospital. Participants will be informed about the trial both written and vocally and no changed in antidiabetic medication will be performed. The instruments will include Corneal Confocal Microscopy (CCM), Quantitative Sensory Testing (QST), axon flair-mediated neurogenic vasodilation (AF), handheld heart rate measurement device (Vagus[™]), cuff, and MRI, which are all established methods of clinical research. Furthermore, participants will be tested using monofilament and Biothesiometry, which equals actual clinical practice, and with Perception Threshold Tracking (PTT), which is a new take on an older, well-known technology. Further tests will include a handheld pinprick device, measurements of peripheral arterial disease (PAD) and conventional NCS. The main endpoint of the study will be sensitivity/specificity of all examinations, as well as a comparison of the newer methods against more well-established modalities.

B. Study Population

The study population include four well-defined groups of subjects:

- 1. Patients with Type 1 diabetes and painful diabetic peripheral neuropathy (DPN).

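### The three-step logistic regression is presented as the guard against mass significance, but no step controls an error rate across measurements and the ANOVA series stays unadjusted

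*Combined protocol and SAP*

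**What the plan says.** Section VI.B (Statistical Methodology) opens with testing: "The data will initially be analyzed by a series ANOVA test to compare each measurement between the four groups". The next sentence names the multiplicity problem and gives the plan's only answer to it: "To avoid 'mass significance' a combined analysis of all measurements will be performed by logistic regression models (LRM) in three steps". The steps are:

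- Step 1: "First, a series of univariate LRM will be performed for each measurement to investigate the odds ratio and accuracy of the individual".
- Step 2: "Second, a multiple factor LRM with all measurements as factors will be performed".
- Step 3: "Thirdly, factor reduction will be performed to assess the accuracy and odds ratio of a set of independent measures".

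Bivariate correlations follow, and then "a further analysis of the interdependency of the measures using factor analysis will be performed". All three regression steps are described as yielding odds ratios and accuracy. This fits section IV.A: "The main endpoint of the study will be sensitivity/specificity of all examinations".

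The only significance level in the document is in section VI.A: "Setting the significance level to 0.05 and the power to 0.8 results in a sample size estimation of 16 persons in each group". Nowhere does the plan give an adjusted level, a testing order, a false-discovery rule, a gating global test or a single primary measurement.

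**The concern.** The plan sees that testing many measurements produces chance findings and says how it will avoid them, but the method named does not do that. Step 1 has the same one-result-per-measurement structure as the ANOVA series it is meant to remedy. Correlations and factor analysis describe how the measures depend on each other; they do not control error.

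At stake is how the results are read. Section X foresees several articles. Unadjusted positive findings could be published with reference to a plan that says mass significance was avoided.

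**Working it through.** **The plan's own figure.** The plan gives no multiplicity figure to reproduce. Its sample size in VI.A does reproduce: 15.7 × (4.7² + 7.5²) / (14.4 − 5.7)² = 15.7 × 78.34 / 75.69 = 16.25, stated as 16; 16 / 0.8 = 20; 4 × 20 = 80. The constant matches 2 × (z for two-sided 0.05 + z for 80% power)² = 15.70. So the level is a two-sided 0.05 for one comparison, with no allowance for several measurements.

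**Number of measurements.** The total is not stated. The documented floor is the 13 sensory-testing (QST) parameters in IV.D. An assumed larger count, built from IV.D, is 13 QST + 2 perception-threshold electrode types + 6 MRI components + 4 Vagus steps + 2 cognitive tests + 4 single tests (pinprick, nerve conduction, corneal microscopy, axon flare) = 31. This is not an upper bound: it leaves out the arm, leg and toe pressures and the toe oxygen measurement.

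**ANOVA series.** Each measurement is tested at 0.05 and all nulls are true. Under independence the chance of at least one false positive is 1 − 0.95^k. The correlated figures come from simulation.

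| Measurements | Independent | Pairwise correlation 0.7 | Expected false positives |
|---|---|---|---|
| 13 | 1 − 0.95^13 = 49% | about 25% | 13 × 0.05 = 0.65 |
| 31 (assumed) | 1 − 0.95^31 = 80% | 37% | 31 × 0.05 = 1.55 |

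**The three steps.** These are simulations with 13 null measurements. The plan does not define the regression outcome, so 40 v 20 (DPN v diabetes without DPN) and 40 v 40 (controls added to the second group) were both assumed.

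- Step 1, any univariate p < 0.05: 31–46% at correlations 0 to 0.5.
- Step 2, any coefficient p < 0.05: about 53–57%.
- Step 3, backward elimination at 0.05 (an assumed rule, since none is given): at least one null measure kept in 46–55%.

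No step comes near 5%.

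**When some measurements do differ.** Assume 10 of 31 independent measures differ by 1.0 SD in both DPN groups, with 16 to 20 per group. The chance of any false positive among the rest is about 66% unadjusted, 26–30% with Benjamini-Hochberg and 4–5% with Holm. The two adjustments control different error rates and cannot be swapped without saying so.

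**Power at the planning effect.** Pooled SD = √(78.34 / 2) = 6.26; effect = 8.7 / 6.26 = 1.39 SD; equal variances assumed. The four-group ANOVA is run at 0.05/31 = 0.0016, Holm's strictest step for 31 measures. The noncentrality is n × the sum of squared deviations of the group means, in SD units.

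- Both DPN groups differ: the sum is 4 × 0.695² = 1.93. Power is 94% at 16 per group and 99% at 20.
- One group differs: the sum is 1.0425² + 3 × 0.3475² = 1.45. Power is 80% at 16 per group and 92% at 20.

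**The case against.** The strongest reply is that the regressions are estimation. The plan describes odds ratios and accuracy, and nothing says a measurement will be declared positive at p < 0.05 from any regression. The study is observational, its main endpoint is sensitivity and specificity, and section VIII concedes that larger studies may be needed to confirm findings. The opening clause can also be read as moving emphasis from many separate tests to a joint model, without promising a formal error rate.

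Much of this stands. It limits the point to the claim of protection and the ANOVA series, and it makes the error rates above conditional on results being read at 0.05. It does not rescue the clause: estimation is a sound aim, but it does not deliver what the clause says. The ANOVA series is testing, and the plan does not label it exploratory.

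A reader might go further in two ways that the documents do not support.

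- A reader might infer that the plan promises familywise control, or intends to declare regression coefficients significant. It says neither.
- A reader might cite failure of the joint model as proof of mass significance. With 31 null predictors about 87% of fits fail at 40 v 20, but only about 2–6% at 40 v 40, and the plan does not say which outcome applies. An overall likelihood-ratio test that rejects too often (10–16% at a nominal 5% with 13 null predictors) reflects too many predictors for the sample. Neither is evidence about multiplicity.

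**Conclusion.** The point holds in this limited form: the plan claims a protection that its analysis does not provide, and it leaves the ANOVA series unadjusted. On the documented floor of 13 measurements, all null and each read at 0.05, the ANOVA series gives at least one false positive with probability between about 25% (correlation 0.7) and 49% (independence).

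The larger figures rest on the assumed count of 31, and the regression figures on an assumed outcome. The conclusion depends on neither, since every setting examined lies far above 5%. The defect affects how results are interpreted, not whether the study can be run. It should be corrected before analysis.

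**What to change.** 1. Delete the statement that the regression steps avoid mass significance. Describe all three as estimation of odds ratio and accuracy. Make no claim of significance from Step 2 coefficients, Step 3 selected measures or the bivariate correlations. State that the intervals are unadjusted and that intervals after selection lack nominal coverage; otherwise an interval excluding an odds ratio of 1 brings the same problem back.
2. List the measurements. Treat the four-group ANOVA p-values, one per measurement, as the single confirmatory family and apply Holm at 5% across it. If the sponsor states that the aim is screening, use Benjamini-Hochberg at a 5% false-discovery rate instead. Name the chosen error rate in the plan.
3. Report univariate regression p-values only if they are adjusted in the same way, as their own stated family.
4. The plan names no pairwise group contrasts; if any are reported, state their adjustment.

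The cost is a few sentences in VI.B, a line of code and lower power per measurement. At the planning effect the loss is modest: power stays at 80% or more even at Holm's strictest step for 31 measures. It is larger for smaller effects. With 10 of 31 independent measures differing by an assumed 1.0 SD in both DPN groups, average power at 16 per group falls from 92% to 80% (Benjamini-Hochberg) or 57% (Holm), and at 20 per group from 97% to 91% or 75%.

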Diabetic peripheral neuropathy (DPN) is the most common complication to advanced diabetes mellitus (DM)[14], and is strongly associated with invalidating and life-threatening complications like foot ulcers[15][16], CN [17][18], painful neuropathy[19], risk of fall and fracture[20], and lower foot amputations[11]. The incidence of DPN is reported with great variance, but several large studies have reported numbers around 20% for DM type I[21][22][23] and 50 % for DM type II[24]. Furthermore, patients with foot pathology attributable to DPN exhibit significantly higher mortality rates than those solely attributable to vascular diseases. This applies to both non-infectious neuropathic foot ulcers[25] and acute CN [26].

At this point no treatment for the underlying nerve damage of DPN is available[27], and the pathogenesis is still not fully understood[28][29][30]. Therefore, current strategies focus on prevention of the initial nerve damage using annual screening-tests targeting large nerve fibers. Available tests for large-fiber function include vibration perception, proprioception, 10-g monofilament, and ankle reflexes[31]. Tests for small-fiber function are not routinely used, but include pinprick and temperature sensation[31]. Most studies have reported that early stages of DPN mainly affect the small nerve fibers[32][33] raising the question of why these are not used in standard screening. However, mixed results do exist, as some studies have reported simultaneous development of DPN in small- and large nerve fibers[34][35]. The most common clinical tests (monofilament) have recently been reviewed, showing low sensitivity when trying to detect early neuropathy[13][36], but wielding fine results when detecting severe neuropathy[37].

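### The logistic models are to be reported by accuracy, which partly reflects the recruitment quotas, and the contrast and cut-off that would yield sensitivity and specificity are not stated

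*Combined protocol and SAP*

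**What the plan says.** Section IV.A makes the sensitivity and specificity of all examinations the main endpoint. Section VI.B plans logistic models in three steps (each measurement alone, all together, a reduced set) and gives their output as follows: "This will allow an estimate of the odds ratio and accuracy of each of the measurements and the measurements in combination". VI.B does not mention sensitivity, specificity, a ROC curve or AUC. It names no binary outcome, no groups entered, no classification cut-off and no reference prevalence.

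The group sizes are quotas. Section VI.A derives 16 per group, inflates to 20 for dropout and multiplies by four: "The total number of participants will therefore be 80". Groups 1 and 2 in IV.B have DPN, group 3 is diabetic without DPN, and group 4 is healthy. For the frequency of DPN, section II.B says that "several large studies have reported numbers around 20% for DM type I"; the sentence words this as incidence and notes that reports vary widely. The limitations in section VIII mention the total of 80 but not the group mix.

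**The concern.** Accuracy is the share of correct classifications, so it averages sensitivity and specificity with the group shares as weights. Those shares were chosen by the investigators. Among diabetic participants DPN makes up 40 of 60, or 67%; in the whole sample it is 40 of 80, or 50%. An accuracy figure therefore describes the recruitment plan as well as the test.

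The cut-off can add a second effect. A logistic intercept carries the log ratio of the groups entered. If predicted probabilities are split at 0.5, an unequal ratio moves the cut-off on the marker scale, and sensitivity and specificity move with it. The shift is larger for weaker markers, which matters in a study meant to compare methods with one another.

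**Working it through.** **Plan's own figure.** Section VI.A: "Setting the significance level to 0.05 and the power to 0.8 results in a sample size estimation of 16 persons in each group". The inputs are SDs 4.7 and 7.5 and means 14.4 and 5.7. The constant 15.7 is 2 × (1.96 + 0.84)² = 15.68, which implies a two-sided test.

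- n = 15.7 × (4.7² + 7.5²) / (14.4 − 5.7)² = 15.7 × 78.34 / 75.69 = 16.25, given as 16.
- 16 / 0.8 = 20 per group, and 4 × 20 = 80. The plan reproduces.

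**Separation implied by the plan.** Pooled SD = √(78.34 / 2) = 6.26, so D = 8.7 / 6.26 = 1.39.

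**Model.** Take one normal marker with equal SDs and a logistic fit without overfitting. Let π be the share with the outcome among those entered. At predicted probability 0.5:

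- sensitivity = Φ(D/2 + logit(π)/D)
- specificity = Φ(D/2 − logit(π)/D)
- accuracy = π × sensitivity + (1 − π) × specificity

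For 40:20, logit(π) = ln 2 = 0.693 and the shift is 0.693 / 1.39 = 0.50. Sensitivity is Φ(0.695 + 0.499) = 0.884 and specificity is Φ(0.695 − 0.499) = 0.578. Accuracy is (2 × 0.884 + 0.578) / 3 = 0.782.

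| Contrast (outcome : comparator) | D | Sensitivity | Specificity | Accuracy in sample |
|---|---|---|---|---|
| 40:20, DPN vs diabetic without DPN | 1.39 | 0.884 | 0.578 | 0.782 |
| 40:20, weaker marker | 0.80 | 0.897 | 0.320 | 0.705 |
| 40:40, DPN vs all without DPN | 1.39 | 0.756 | 0.756 | 0.756 |
| 20:20, any two groups | 1.39 | 0.756 | 0.756 | 0.756 |
| 20:60, one group vs the rest | 1.39 | 0.462 | 0.931 | 0.814 |

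The last row uses ln(1/3) / 1.39 = −0.79, and its accuracy is (0.462 + 3 × 0.931) / 4. It treats the three pooled groups as one normal population, so it shows direction only. Even dropout to 32:16 leaves the 40:20 results unchanged.

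**Same 40:20 rule at other DPN frequencies (D = 1.39).** At 20%: 0.2 × 0.884 + 0.8 × 0.578 = 0.639. At 10%, 30% and 50%: 0.608, 0.670 and 0.731. Calling everyone positive scores 40/60 = 67% in the sample and 20% at 20% DPN.

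**Check by simulation.** With 1,500 fitted models per setting, 40:20 gave 0.89/0.58 and 40:40 gave 0.76/0.76. The plan does not say which SD belongs to which group. With SDs 4.7 and 7.5 in either order, 40:20 gave sensitivity 0.86 to 0.92 and specificity 0.56 to 0.61.

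**Effect of a neutral cut-off.** Subtracting ln 2 from the 40:20 intercept and classifying at 0.5 is the same as using 2/3 on the unadjusted fit. It returns 0.756/0.756. The AUC is 0.837 at every ratio.

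**The case against.** The strongest reply is that the plan states neither the 40:20 contrast nor the 0.5 cut-off. The sample size compares one group with one group (20:20), and DPN against everyone without it is 40:40. In both, with equal SDs, sensitivity, specificity and accuracy are all 76%, and accuracy is then the same at every prevalence. This stands, so the figures for 40:20 are a conditional example.

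Three stronger readings are tempting, and the documents do not support them.

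- A reader might infer that every sensitivity and specificity in the study depends on group sizes. VI.B does not say they come from model classification. At a fixed marker value, a Youden point or a cut-off equal to the sample share, they do not depend on group sizes in expectation.
- A reader might infer that the design favours sensitivity. That needs 40:20 and 0.5 together; the 20:60 contrast reverses it.
- A reader might infer that accuracy will be overstated for clinic use. The fall from 78% to 64% comes from carrying one rule unchanged to 20% DPN. The same marker refitted at 20% DPN has accuracy 84%, which is higher. The plan makes no claim about accuracy at clinic prevalence.

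It can also be said that all tests face the same mix, so their comparison is fair. This holds for the order of accuracy (0.782 against 0.705). It fails for sensitivity: under 40:20 and 0.5 the 0.8 SD marker shows 90% against 88% for the better one, and the difference surfaces only in specificity (32% against 58%).

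**Conclusion.** The point holds in a limited form. VI.B chooses a performance measure weighted by recruitment quotas and does not say how the main endpoint will be obtained. Depending on an unstated contrast and cut-off, a marker of the plan's own strength could be reported as 88%/58% or 76%/76%, and an unequal contrast the other way would favour specificity. Under 40:20 and 0.5, the 78% sample accuracy is only 11 points above the 67% from calling everyone positive, and the same rule gives 61% to 73% at 10% to 50% DPN.

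These sizes assume one normal marker, the 1.39 SD separation from VI.A and no overfitting. The 20% from II.B is an incidence figure used as a stand-in for prevalence, which is why a range is shown. This is an inexpensive improvement to the SAP; it does not invalidate the design.

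**What to change.** In VI.B:

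1. Name the binary outcome and the groups entered for each logistic model.
2. Replace raw accuracy as the performance measure with AUC plus sensitivity and specificity, each with a confidence interval.
3. Pre-specify a cut-off rule whose result does not depend on the sample share. Either fix specificity at a stated value, or subtract the log sampling ratio from the intercept (ln 2 for 40:20) before classifying at 0.5.
4. If accuracy is reported, give it only at stated DPN prevalences over a range, for example 10% to 50% including the 20% in II.B.

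The cost is SAP wording and slightly more analysis, with no added participants or tests. Headline figures may look less favourable, and the intervals will show how little 20 non-DPN diabetic participants can say about specificity: at 0.756 the approximate 95% half-width is 1.96 × √(0.756 × 0.244 / 20) = 0.19.
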